**1. Definitions of image-related events**

At each follow-up imaging visit (each value of FIMG:CPEVENT), each patient is classified as follows:

endoleak, any

yes if	on follow-up fenestrated imaging form, endoleak = yes (FIMG:ENDOYN = "YES")
no if	on follow-up fenestrated imaging form, endoleak = no (FIMG:ENDOYN = "NO")
missing otherwise	

endoleak, type I

yes if	on follow-up fenestrated imaging form, type I is checked (FIMG:ENDTYP1 = 1)
no if	on follow-up fenestrated imaging form, endoleak has been answered (FIMG:ENDOYN = "YES" or FIMG:ENDOYN = "NO") AND
	on follow-up fenestrated imaging form, type I is not checked (FIMG:ENDTYP1 = NULL)
missing otherwise	

endoleak, type II

yes if	on follow-up fenestrated imaging form, type II is checked (FIMG:ENDTYP2 = 1)
no if	on follow-up fenestrated imaging form, endoleak has been answered (FIMG:ENDOYN = "YES" or FIMG:ENDOYN = "NO") AND
	on follow-up fenestrated imaging form, type II is not checked (FIMG:ENDTYP2 = NULL)
missing otherwise	

endoleak, type III

yes if	on follow-up fenestrated imaging form, type III is checked (FIMG:ENDTYP3 = 1)
no if	on follow-up fenestrated imaging form, endoleak has been answered (FIMG:ENDOYN = "YES" or FIMG:ENDOYN = "NO") AND
	on follow-up fenestrated imaging form, type III is not checked (FIMG:ENDTYP3 = NULL)
missing otherwise	

endoleak, type IV

yes if	on follow-up fenestrated imaging form, type IV is checked (FIMG:ENDTYP4 = 1)
no if	on follow-up fenestrated imaging form, endoleak has been answered (FIMG:ENDOYN = "YES" or FIMG:ENDOYN = "NO") AND
	on follow-up fenestrated imaging form, type IV is not checked (FIMG:ENDTYP4 = NULL)
missing otherwise	

endoleak, unknown

yes if	on follow-up fenestrated imaging form, unknown is checked (FIMG:ENDTYP5 = 1)
no if	on follow-up fenestrated imaging form, endoleak has been answered (FIMG:ENDOYN = "YES" or FIMG:ENDOYN = "NO") AND
	on follow-up fenestrated imaging form, unknown is not checked (FIMG:ENDTYP5 = NULL)
missing otherwise	

growth notation:

- A1\_p = maximum aneurysm diameter major axis on follow-up fenestrated imaging form (FIMG:DIAMEA1) at pre-discharge visit

- A1\_c = maximum aneurysm diameter major axis on follow-up fenestrated imaging form (FIMG:DIAMEA1) at current visit
- A2\_p = maximum aneurysm diameter minor axis on follow-up fenestrated imaging form (FIMG:DIAMEA2) at pre-discharge visit
- A2\_c = maximum aneurysm diameter minor axis on follow-up fenestrated imaging form (FIMG:DIAMEA2) at current visit

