	on follow-up fenestrated KUB form, left iliac leg extension stent fracture = "YES" (FKUB:DISF8 = "YES") OR
	on follow-up fenestrated KUB form, main body extension stent fracture = "YES" (FKUB:DISF9 = "YES") OR
	on follow-up fenestrated KUB form, renal stent right stent fracture = "YES" (FKUB:DISF10 = "YES") OR
	on follow-up fenestrated KUB form, renal

	stent left stent fracture = "YES" (FKUB:DISF11 = "YES") OR
	on follow-up fenestrated KUB form, other stent fracture = "YES" (FKUB:DISF12 = "YES")
no if	on follow-up fenestrated KUB form, proximal graft stent fracture = "NO" or "N/A" (FKUB:DISF1 = "NO" or "N/A") AND
	on follow-up fenestrated KUB form, distal graft stent fracture = "NO" or "N/A" (FKUB:DISF2 = "NO" or "N/A") AND
	on follow-up fenestrated KUB form, right iliac stent fracture = "NO" or "N/A" (FKUB:DISF3 = "NO" or "N/A") AND
	on follow-up fenestrated KUB form, left iliac stent fracture = "NO" or "N/A" (FKUB:DISF4 = "NO" or "N/A") AND
	on follow-up fenestrated KUB form, occluder stent fracture = "NO" or "N/A" (FKUB:DISF5 = "NO" or "N/A") AND
	on follow-up fenestrated KUB form, converter stent fracture = "NO" or "N/A" (FKUB:DISF6 = "NO" or "N/A") AND
	on follow-up fenestrated KUB form, right iliac leg extension stent fracture = "NO" or "N/A" (FKUB:DISF7 = "NO" or "N/A") AND
	on follow-up fenestrated KUB form, left iliac leg extension stent fracture = "NO" or "N/A" (FKUB:DISF8 = "NO" or "N/A") AND
	on follow-up fenestrated KUB form, main body extension stent fracture = "NO" or "N/A" (FKUB:DISF9 = "NO" or "N/A") AND
	on follow-up fenestrated KUB form, renal stent right stent fracture = "NO" or "N/A" (FKUB:DISF10 = "NO" or "N/A") AND
	on follow-up fenestrated KUB form, renal stent left stent fracture = "NO" or "N/A" (FKUB:DISF11 = "NO" or "N/A") AND
	on follow-up fenestrated KUB form, other stent fracture = "NO" or "N/A" (FKUB:DISF12 = "NO" or "N/A")
missing otherwise	

barb fracture

yes if	on follow-up fenestrated KUB form, barb bend is checked (FKUB:PFSNIN1 = 1) OR
	on follow-up fenestrated KUB form, proximal stent separation is checked (FKUB:PFSNIN3 = 1) OR
	on follow-up fenestrated KUB form, barb separation is checked (FKUB:PFSNIN2 = 1)
no if	on follow-up fenestrated KUB form, barb bend is not checked (FKUB:PFSNIN1 = NULL) AND
	on follow-up fenestrated KUB form, proximal stent separation is not checked (FKUB:PFSNIN3 = NULL) AND
	on follow-up fenestrated KUB form, barb separation is not checked (FKUB:PFSNIN2 = NULL)
missing otherwise	

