component separation

yes if	on follow-up fenestrated KUB form, "Has component separation of the endovascular graft occurred?" = "YES" (FKUB:COMSYN = "YES")
no if	on follow-up fenestrated KUB form, "Has component separation of the endovascular graft occurred?" = "NO" (FKUB:COMSYN = "NO")
missing otherwise	

compression

yes if	on follow-up fenestrated KUB form, renal stent right compression = "YES" (FKUB:DEVCPR1 = "YES") OR
	on follow-up fenestrated KUB form, renal stent left compression = "YES" (FKUB:DEVCPR2 = "YES") OR
	on follow-up fenestrated KUB form, other stent compression = "YES" (FKUB:DEVCPR3 = "YES")
no if	on follow-up fenestrated KUB form, renal

	stent right compression = "NO" or "N/A" (FKUB:DEVCPR1 = "NO" or "N/A") AND
	on follow-up fenestrated KUB form, renal stent left compression = "NO" or "N/A" (FKUB:DEVCPR2 = "NO" or "N/A") AND
	on follow-up fenestrated KUB form, other stent compression = "NO" or "N/A" (FKUB:DEVCPR3 = "NO" or "N/A")
missing otherwise	

occlusion, right iliac artery CIA

yes if	on follow-up fenestrated imaging form, right iliac artery patent CIA = "YES" (FIMG:PATCIA1 = "NO")
no if	on follow-up fenestrated imaging form, right iliac artery patent CIA = "YES" (FIMG:PATCIA1 = "YES")
missing otherwise	

occlusion, right iliac artery IIA

yes if	on follow-up fenestrated imaging form, right iliac artery patent IIA = "YES" (FIMG:PATIIA1 = "NO")
no if	on follow-up fenestrated imaging form, right iliac artery patent IIA = "YES" (FIMG:PATIIA1 = "YES")
missing otherwise	

occlusion, left iliac artery CIA

yes if	on follow-up fenestrated imaging form, left iliac artery patent CIA = "YES" (FIMG:PATCIA2 = "NO")
no if	on follow-up fenestrated imaging form, left iliac artery patent CIA = "YES" (FIMG:PATCIA2 = "YES")
missing otherwise	

occlusion, left iliac artery IIA

yes if	on follow-up fenestrated imaging form, left iliac artery patent IIA = "YES"
--------	--

	(FIMG:PATIIA2 = "NO")
no if	on follow-up fenestrated imaging form, left iliac artery patent IIA = "YES" (FIMG:PATIIA2 = "YES")
missing otherwise	

occlusion, right renal

yes if	on follow-up fenestrated imaging form, right renal occluded is checked (FIMG:PATRRA = "OCCLUDED")
no if	on follow-up fenestrated imaging form, right renal patent is checked (FIMG:PATRRA = "PATENT")
missing otherwise	

occlusion, left renal

yes if	on follow-up fenestrated imaging form, left renal occluded is checked (FIMG:PATLRA = "OCCLUDED")

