### 3. Summary reports for events

At selected visits, the following is reported for each event:

1. number of subjects with event = yes
2. (number of subjects with event = yes) + (number of subjects with event = no)

The selected visits are as follows:

- pre-discharge (FIMG/FUP:CPEVENT = "PRE\_DISCHARGE")
- 1 month (FIMG/FUP:CPEVENT = "1 MONTH FUP")
- 6 months (FIMG/FUP:CPEVENT = "6 MONTH FUP")
- 12 months (FIMG/FUP:CPEVENT = "12 MONTH FUP")
- 24 months (FIMG/FUP:CPEVENT = "24 MONTH FUP")
- 36 months (FIMG/FUP:CPEVENT = "3 YEAR FUP")
- 48 months (FIMG/FUP:CPEVENT = "4 YEAR FUP")
- other (FIMG/FUP:CPEVENT = "OTHER")

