## 7.2. Events: Summary report

All events will be included in a single report, which will have one column for each visit and two rows for each event, as follows:

event		pre-discharge	visit 1-month	(etc.)
endoleak, any	number yes	#	#	
	number yes or no	#	#	
endoleak, type I	number yes	#	#	
	number yes or no	#	#	
(etc.)				

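### The barb-fracture rule counts three blank checkboxes as a negative reading, so KUB forms on which the barbs were never assessed can enter the denominator

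*SAP*

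**What the plan says.** SAP Section 1 sets the unit of classification: "At each follow-up imaging visit (each value of FIMG:CPEVENT), each patient is classified as follows".

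For barb fracture, *yes* needs any one of three KUB checkboxes to be ticked, starting with "barb bend is checked (FKUB:PFSNIN1 = 1) OR" and continuing with proximal stent separation (PFSNIN3) and barb separation (PFSNIN2). *No* needs all three to be NULL, ending with "barb separation is not checked (FKUB:PFSNIN2 = NULL"). A final row assigns *missing* to anything else.

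The endoleak types in the same section are also checkboxes coded 1 or NULL. There, a blank box counts as *no* only with an added condition: "endoleak has been answered (FIMG:ENDOYN = 'YES' or FIMG:ENDOYN = 'NO') AND" the box is not ticked.

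The other three KUB events need explicit answers before they can be *no*: stent fracture needs NO or N/A in 12 fields, component separation needs COMSYN = NO, and compression needs NO or N/A in three fields.

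Section 3 reports the number *yes* and then the sum ("number of subjects with event = yes) + (number of subjects with event = no"). Section 7.2 shows that sum as the row "number yes or no". Section 7.3 allows 0, 1 or missing for each subject and visit.

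**The concern.** A tick-if-present box left blank can mean that the reader looked and found nothing, or that nobody looked. The barb rule treats both as a negative finding. It has a *missing* row, but no combination of the three box values leads to it.

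What is at stake is the denominator of a device-integrity event. Unassessed subjects add nothing to the *yes* count and add to the *yes*-or-*no* count. A reader who divides one by the other gets a proportion that is too low. Where there are no events, the reader sees a zero that appears to rest on more readings than were made.

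The audit in Section 6 need not expose this. It compares derived data with the data-capture screens, and a blank coded *no* is what the rule prescribes.

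**Working it through.** The SAP states no rate, sample size or completeness figure on this point, so there is no figure to reproduce. The check has two parts.

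**1. Apply each rule to every possible field state.** The rules and field codings come from SAP Section 1; NULL is included as a possible value of every field.

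| Event | Possible states | *yes* | *no* | *missing* | All fields blank |
|---|---|---|---|---|---|
| Barb fracture (3 boxes, 1/NULL) | 2³ = 8 | 7 | 1 | 0 | *no* |
| Endoleak type (ENDOYN YES/NO/NULL × box 1/NULL) | 3 × 2 = 6 | 3 | 2 | 1 | *missing* |
| Component separation (YES/NO/NULL) | 3 | 1 | 1 | 1 | *missing* |
| Compression (3 fields, YES/NO/N/A/NULL) | 4³ = 64 | 64 − 3³ = 37 | 2³ = 8 | 27 − 8 = 19 | *missing* |
| Stent fracture (12 fields, same coding) | 4¹² = 16,777,216 | 4¹² − 3¹² = 16,245,775 | 2¹² = 4,096 | 3¹² − 2¹² = 527,345 | *missing* |

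A single KUB form with all these fields blank is therefore *missing* for stent fracture, component separation and compression, and *no* for barb fracture.

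**2. Effect on the reported counts.** Let Y be the number *yes*, A the number assessed, and U the number unassessed but coded *no*. Put p = Y/A and f = U/(A + U). Then

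reported proportion = Y/(A + U) = p × A/(A + U) = p(1 − f).

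The SAP gives neither p nor f. Taking p = 5% as an assumption:

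| f (assumed) | p(1 − f) |
|---|---|
| 0 | 5.0% |
| 10% | 4.5% |
| 20% | 4.0% |
| 40% | 3.0% |

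In counts, with 100 subjects, 80 assessed and 4 events: 4/80 = 5.0% if the unassessed are excluded, 4/100 = 4.0% under the rule as written.

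With no events, 60 assessed out of 100 would be shown as 0/100 instead of 0/60. The exact two-sided 95% upper limit for 0/n is 1 − 0.025^(1/n), which is 6.0% for n = 60 and 3.6% for n = 100. The SAP plans no interval for these events; the limits only show how much apparent evidence the blanks can add.

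**The case against.** There are four points on the other side.

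- **The form must exist.** Each *no* condition refers to a box on the KUB form. Read plainly, a box can be unticked only on a form that exists, so a visit without one would be *missing*, and the *missing* row would have a use. This is a fair reading, and it limits the no-form case. It does not help a submitted form with a blank barb item. The endoleak rules carry the same kind of form reference and still add the answered-question condition. Nor does the SAP secure the reading: visits are keyed on FIMG (or FIMG/FUP), the date cut-off in Section 7.1 names only FIMG and FUP dates, and no FKUB visit key or join is given. If KUB fields are joined to imaging visits, an absent form yields three NULLs and is coded *no*. That branch remains conditional on the programming.
- **The form is not shown.** It may carry a lead question, an instruction that blank means none, or entry checks. Treating an unticked box on a completed form as absent is an ordinary convention. This stands as a limit on the size of the effect. But the rule as written uses no such safeguard.
- **The figures are assumed, and only counts are reported.** This is true. No proportion is planned and the *yes* count is right. The affected quantity is one denominator for one descriptive event.
- **The fallback field is imperfect.** COMSYN concerns component separation, not barbs. This stands, and its limits are set out with the fix.

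**Conclusion.** The concern holds. As written, the barb-fracture rule cannot separate an unread item from a negative one on a submitted KUB form, and it departs from the standard the SAP applies to its other checkbox and KUB events. Any error runs one way: the *yes*-or-*no* count can be too large, never too small for this reason, and the implied proportion is lowered by the factor (1 − f).

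The logic of the rule is certain from the text; the size is not. It depends on how often KUB forms were submitted with the barb item unassessed and, if the tables are joined that way, on how often an imaging visit had no KUB form. No test or performance goal depends on this event here, so the consequence is confined to descriptive device-integrity reporting. It should be fixed.

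**What to change.** Rewrite the *no* row so that it requires all of the following, with *missing* otherwise:

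1. an FKUB record exists for that visit;
2. there is evidence that the form was read;
3. PFSNIN1, PFSNIN2 and PFSNIN3 are all NULL.

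For item 2, use a lead question on the barbs or proximal fixation if the form has one; the SAP names none, so the case report form must be checked. Failing that, require COMSYN = YES or NO, and state in the SAP that this is a proxy for form completion and does not prove that the barbs were read. With the proxy, the 3 × 8 = 24 states divide into 21 *yes*, 2 *no* and 1 *missing*, and the all-blank form becomes *missing*, as it is for the other KUB events.

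Add one sentence saying that a visit with no FKUB record is *missing* for all KUB events.

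The cost is one or two lines of SAP text and code. The denominator may shrink and the proportion look slightly less favourable. The COMSYN proxy would still count some unread barb items as *no*, and would drop a subject whose barbs were read but whose COMSYN field was left blank.

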## 2. Definitions of non-image-related events

At each follow-up visit (each value of FUP:CPEVENT) after the first follow-up visit, each patient is classified as follows:

creatinine notation:

- $C_b$  = creatinine on subject history form (LABS:LABCRE)
- $C_f$  = creatinine on follow-up form (FUP:LABCRE) at current visit
- $C_p$  = creatinine on follow-up form (FUP:LABCRE) at previous visit

creatinine rise

yes if	$(C_f - C_b) / C_b > 0.30$ AND
	$(C_p - C_b) / C_b > 0.30$
no if	$(C_f - C_b) / C_b \leq 0.30$ OR
	$(C_p - C_b) / C_b \leq 0.30$
missing otherwise	

### 3. Summary reports for events

At selected visits, the following is reported for each event:

1. number of subjects with event = yes
2. (number of subjects with event = yes) + (number of subjects with event = no)

The selected visits are as follows:

- pre-discharge (FIMG/FUP:CPEVENT = "PRE\_DISCHARGE")
- 1 month (FIMG/FUP:CPEVENT = "1 MONTH FUP")
- 6 months (FIMG/FUP:CPEVENT = "6 MONTH FUP")
- 12 months (FIMG/FUP:CPEVENT = "12 MONTH FUP")
- 24 months (FIMG/FUP:CPEVENT = "24 MONTH FUP")
- 36 months (FIMG/FUP:CPEVENT = "3 YEAR FUP")
- 48 months (FIMG/FUP:CPEVENT = "4 YEAR FUP")
- other (FIMG/FUP:CPEVENT = "OTHER")

## **4. Mortality**

### **4.1. General**

Each patient will have a follow-up time, defined as follows:

- = months from initial procedure date (PRTH:PROC DT such that PRTH:PROTYP = “INIT IMPLANT”) to death date (DTH:DTHDAT), if known to be dead
- = months from initial procedure date (PRTH:PROC DT such that PRTH:PROTYP = “INIT IMPLANT”) to last day of reporting period, if not known to be dead

A month will be defined as 30 days.

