## 4.2. All-cause

All-cause mortality will be summarized in the following table:

	Follow-up time						
	1 month	6 months	12 months	24 months	36 months	48 months	60 months
Alive and in study a							
Dead to date b	before discharge: c						
	after discharge: f						
Censored to date c							
Survival probability d							

aNumber of subjects whose follow-up times are greater than the time point.

bNumber of subjects whose follow-up times are less than or equal to the time point and who are known to be dead.

cNumber of subjects whose follow-up times are less than or equal to the time point and who are not known to be dead.

dThe Kaplan-Meier estimate of the survival curve at the time point, with 95-percent confidence interval. The survival curve gives the probability of surviving past a given time.

eNumber of subjects in this cell whose deaths occurred before discharge (PRTH:DSCHDT).

fNumber of subjects in this cell whose deaths occurred after discharge (PRTH:DSCHDT).

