### 4.3. AAA-related

Deaths will be classified as AAA-related based on the following definition:

yes if	death occurs within 30 days of any procedure (initial or secondary) OR
	on the death form, “procedure caused or contributed to death” = yes (DTH:DTCYNP = “YES” and DTH:DTHCTX = “PROCEDURE CAUSED OR CONTRIBUTED TO DEATH”) OR
	on the death form, “device caused or contributed to death” = yes (DTH:DTCYNP = “YES” and DTH:DTHCTX = “DEVICE CAUSED OR CONTRIBUTED TO DEATH”)
no if	death does not occur within 30 days of any procedure (initial or secondary) AND
	on the death form, “procedure caused or contributed to death” = no (DTH:DTCYNP = “NO” and DTH:DTHCTX = “PROCEDURE CAUSED OR CONTRIBUTED TO DEATH”) AND
	on the death form, “device caused or contributed to death” = no (DTH:DTCYNP = “NO” and DTH:DTHCTX = “DEVICE CAUSED OR CONTRIBUTED TO DEATH”)
missing otherwise	

AAA-related mortality will be summarized in the following table:

	Follow-up time						
	1 month	6 months	12 months	24 months	36 months	48 months	60 months
Alive and in study a							
Dead of AAA to date b	before discharge: e						
	after discharge: f						
Censored to date c							
Survival probability d							

aNumber of subjects whose follow-up times are greater than the time point.

bNumber of subjects whose follow-up times are less than or equal to the time point, who are known to be dead, and whose deaths are AAA-related.

cNumber of subjects whose follow-up times are less than or equal to the time point and who are not known to be dead, are dead of a cause unrelated to AAA, or are dead of an unknown cause.

dThe Kaplan-Meier estimate of the survival curve at the time point, with 95-percent confidence interval. The survival curve gives the probability of surviving past a given time.

eNumber of subjects in this cell whose deaths occurred before initial discharge (PRTH:DSCHDT such that PRTH:PROTYP = "INIT IMPLANT").

fNumber of subjects in this cell whose deaths occurred after initial discharge (PRTH:DSCHDT such that PRTH:PROTYP = "INIT IMPLANT").

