## 5. Secondary interventions

Each patient will have a follow-up time, defined as follows:

- = months from date of initial procedure (PRTH:PROCDT such that PRTH:PROTYP = “INIT IMPLANT”) to date of first secondary intervention (PRTH:PROCDT such that PRTH:PROTYP = “ADD ENDO”), if any secondary interventions
- = months from initial procedure date (PRTH:PROCDT such that PRTH:PROTYP = “INIT IMPLANT”) to death date (DTH:DTHDAT), if no secondary interventions and known to be dead
- = months from initial procedure date (PRTH:PROCDT such that PRTH:PROTYP = “INIT IMPLANT”) to last day of reporting period, if no secondary interventions and not known to be dead

A month will be defined as 30 days.

Secondary interventions will be summarized in the following table:

	Follow-up time						
	1 month	6 months	12 months	24 months	36 months	48 months	60 months
Alive, in study, and free of secondary interventions a							
Has experienced at least one secondary intervention b							
Censored to date c							
Survival probability d							

aNumber of subjects whose follow-up times are greater than the time point.

bNumber of subjects whose follow-up times are less than or equal to the time point and who experienced at least one secondary intervention.

cNumber of subjects whose follow-up times are less than or equal to the time point and and who have not experienced any secondary interventions.

dThe Kaplan-Meier estimate of the survival curve at the time point, with 95-percent confidence interval. The survival curve gives the probability of surviving past a given time.

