## 7. Web reports

### 7.1. General

All reports are available in Excel or PDF format and can be limited in any of the following ways:

1. whether to exclude compassionate use cases (default: do not exclude)
  - a. exclude (CLNO:COMPYN = "NO")
  - b. do not exclude (all cases)
2. type of device (default: all subjects):
  - a. fenestrated (PRTH:FORMTP1 = 1)
  - b. visceral (PRTH:FORMTP2 = 1)
  - c. hypogastric (PRTH:FORMTP3 = 1)
3. maximum subject number (default: all subjects)
4. maximum enrollment date (default: date on which the report is generated), which has the following effects:
  - a. a subject can be included only if his procedure date (PRTH:PROCDT) is less than or equal to the maximum
  - b. a follow-up form can be used only if the visit date (FIMG:APPTDT or FUP:EV\_DT) is less than or equal to the maximum
  - c. a subject can be counted as dead only if his death date (DTH:DTHDAT) is less than or equal to the maximum
  - d. a secondary intervention can be counted only if the procedure date (PRTH:PROCDT) is less than or equal to the maximum
  - e. the maximum is considered the last day of the reporting period in the definitions of follow-up time in sections 4 and 5

Events are reported at the following visits:

- pre-discharge (FIMG/FUP:CPEVENT = "PRE\_DISCHARGE")
- 1 month (FIMG/FUP:CPEVENT = "1 MONTH FUP")
- 6 months (FIMG/FUP:CPEVENT = "6 MONTH FUP")
- 12 months (FIMG/FUP:CPEVENT = "12 MONTH FUP")
- 24 months (FIMG/FUP:CPEVENT = "24 MONTH FUP")
- 36 months (FIMG/FUP:CPEVENT = "3 YEAR FUP")
- 48 months (FIMG/FUP:CPEVENT = "4 YEAR FUP")
- other (FIMG/FUP:CPEVENT = "OTHER")

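### Sections 4.1 and 5 run follow-up of every subject without a recorded event to one common report date, so lost subjects stay at risk and are counted as in study; the Kaplan-Meier estimates are biased upward if their later events are not fully captured

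*SAP*

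**What the plan says.** Section 4.1 has two branches. A subject known to be dead is followed to the death date; any other subject is followed "to last day of reporting period, if not known to be dead". Section 5 has three: the first secondary intervention, else death, else "to last day of reporting period, if no secondary interventions and not known to be dead".

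Section 7.1, item 4e, fixes the end date for the web reports: "the maximum is considered the last day of the reporting period in the definitions of follow-up time in sections 4 and 5". That maximum is a report setting, described as "maximum enrollment date (default: date on which the report is generated".

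The tables build on these times. The in-study row of section 4.2 is defined as "Number of subjects whose follow-up times are greater than the time point", and section 5 labels its counterpart "Alive, in study, and free of secondary interventions". The censored row of section 4.2 is "Number of subjects whose follow-up times are less than or equal to the time point and who are not known to be dead". In section 4.3 it covers those "who are not known to be dead, are dead of a cause unrelated to AAA, or are dead of an unknown cause". Each table then gives a Kaplan-Meier estimate with a 95% interval at 1 to 60 months.

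No rule in sections 4, 5 or 7 uses a date of withdrawal, loss, last visit or last contact.

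**The concern.** The branches together cover every subject, so there is no gap for another rule to fill. Having no recorded event is treated as being observed event-free up to the report date, whether or not status is known to that date.

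Two things follow. First, a lost or withdrawn subject remains in the risk set, appears in the in-study row, and reaches the censored row only when the report date is reached. The tables cannot show loss at all. Second, if some deaths or interventions after loss never reach the database, the denominator keeps subjects who can no longer contribute an event. Survival and freedom from secondary intervention then look better than they are, with the distortion growing over time. For long-term results on a device, that is the unfavourable direction in which to be wrong.

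**Working it through.** The SAP states no sample size, event rate, loss rate or capture rate, so there is no planned figure to reproduce. The rates below are assumptions.

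**What the rule does to one subject.** Take a subject implanted 2,190 days before the report date and lost at day 180. With the SAP's 30-day month, follow-up is 2190/30 = 73.0 months. Loss came at 180/30 = 6.0 months, so 67 months lie after loss. The subject is counted as in study at 12, 24, 36, 48 and 60 months and is in the censored row of none of the table's columns.

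**Effect on the estimate.** Assume a constant event hazard h, an independent loss hazard l, and a share c of events after loss that is captured. Under the plan only the report date censors (and death, in section 5), so the curve estimates one minus the probability of a *recorded* event by time t:

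- truth: exp(−ht)
- events before loss: q = [h/(h+l)] × (1 − exp(−(h+l)t))
- plan: S = 1 − {q + c[(1 − truth) − q]}

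All-cause death, h = 0.08, l = 0.05, t = 5 years:

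- truth = exp(−0.40) = 0.6703
- q = (0.08/0.13) × (1 − exp(−0.65)) = 0.6154 × 0.4780 = 0.2941
- c = 0: S = 0.7059, overstated by 3.56 points
- c = 0.5: overstated by 1.78 points
- c = 1: overstated by 0

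Secondary intervention, h = 0.05, l = 0.05, t = 5 years, with deaths at 6% per year all captured and censoring independently, so the same formula holds:

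- truth = exp(−0.25) = 0.7788
- q = 0.5 × (1 − exp(−0.50)) = 0.1967
- c = 0: S = 0.8033, overstated by about 2.4 points
- c = 0.5: about 1.2 points
- c = 1: 0

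Range for all-cause death at 60 months (points overstated):

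| Yearly loss | none captured | half | all |
|---|---|---|---|
| 2% | 1.5 | 0.7 | 0 |
| 5% | 3.6 | 1.8 | 0 |
| 10% | 6.6 | 3.3 | 0 |

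For AAA-related death (assumed 2% perioperative, then 0.5 to 1% per year) the overstatement with no capture is only 0.1 to 1.0 points. At 1 year, even with 10% yearly events and 10% yearly loss, the all-cause bias is at most 0.5 point.

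**Effect on the interval.** Simulation with assumed N = 150, potential follow-up uniform over 12 to 96 months, h = 0.08 and l = 0.05 gives this coverage of the 95% interval:

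| Capture | plain | log-log |
|---|---|---|
| none | 85% | 89% |
| half | 91% | 94% |
| all | 94% | 95% |

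With no capture the mean Greenwood standard error (0.0436) matches the empirical one (0.0440). The shortfall comes from centring, not from the standard error.

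**Effect on the label.** In the same setting with every death captured, 150 × 3/7 × 0.6703 ≈ 43 subjects are shown as in study at 60 months. Of these, 43 × (1 − exp(−0.25)) ≈ 9.5 have already left.

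**The case against.** The strongest objection is that harm depends on something the SAP does not show. Running everyone to a common date is legitimate when status is ascertained to that date, and tracing of lost subjects is commonly described in the protocol, which is not at hand. This stands as a limit on the claim: a reader might infer that the planned curves are biased as written, and the document does not support that. It does not remove the point, because the SAP states its own complete rule and applies it whether or not status is known.

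A reader might also infer that the default end date, the day the report is run, is a separate fault. It is only a default. The user can set another date, and items 4a to 4d of section 7.1 apply the same limit to procedures, forms, deaths and interventions.

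The sizes rest wholly on assumed rates, and the milder ones are small: 0.7 points at 2% loss with half the deaths captured, against an interval half-width of about 8.5 to 8.9 points in the 5% loss simulation.

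Finally, censoring at loss is not always better. At 5% loss, if the death rate after loss is halved, it is off by −1.7 points, and the present rule with half capture by +1.0. If the rate is doubled, the figures are +2.7 and +3.1. This stands, and is why the fix keeps both analyses.

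**Conclusion.** The point holds in conditional form and should be fixed. Certain from the text: follow-up without a recorded event runs to one report date, the in-study rows are not tied to study status, and loss is invisible in the tables. Conditional: if subjects are lost and their later events are incompletely captured, all the Kaplan-Meier curves are biased upward and their intervals under-cover. With full ascertainment to the report date the estimates are unbiased.

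Under constant hazards, independent loss and 5% yearly loss, the 60-month overstatement is 3.6, 1.8 or 0 points for all-cause survival (8% deaths per year), and about 2.4, 1.2 or 0 points for freedom from secondary intervention (5% per year), with none, half or all later events captured. The actual size cannot be determined from the SAP.

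**What to change.** In sections 4.1 and 5, end follow-up at the earliest of the event, a fixed data cut-off, and the date to which the subject's status is known.

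- Where status has been checked for all subjects to the cut-off, including lost ones, the present rule with that fixed cut-off stands. This is the preferable route.
- Otherwise censor withdrawn or lost subjects at the date of withdrawal or loss or, failing that, at last documented contact (FUP:EV_DT or FIMG:APPTDT). Apply this alike to subjects with and without later events, and list events after that date. Censoring only the event-free at last contact while still counting later known deaths errs the other way: 0.573 against a true 0.591 in a simulation with 10% yearly events, 5% yearly loss and half capture.
- Keep censoring at death in section 5.
- Report the present rule, which counts all known later events, alongside as a sensitivity analysis, since neither rule is uniformly less biased under partial capture and informative loss.
- Relabel the in-study rows and add a row for subjects withdrawn or lost to date.

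Costs: SAP wording, one derived date, changed footnotes, and updates to the web reports and the audited derived data sets. The SAP names no loss-date field, so visit dates may have to serve; in simulation that shifts the estimate down by about 0.5 point at 5% loss. Censoring at loss also widens the interval somewhat (half-width about 9.7 points against 8.5 to 8.9), may give less favourable estimates, and relies on loss being independent of the event.
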